## **16.6. Immune Tolerance Induction**

For each subject undergoing ITI, the outcome (complete success, partial success, failure, and early withdrawal during the monitoring period will be listed and summarized. Additional summaries, including the percentage of subjects with relapse (as defined in Section 10.2.7.6), will be documented in the study SAP.

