2.2.2. Secondary Endpoints

The secondary endpoints of the study are as follows:

- The annualized number of bleeding episodes per patient (annualized bleeding rate [ABR])
- The annualized number of spontaneous joint bleeding episodes per patient.
- Assessments of response to treatment with rFVIII Fc for bleeding episodes, using the 4-point bleeding response scale.
- The total number of EDs per patient per year
- Total annualized rFVIII Fc consumption per patient for the prevention and treatment of bleeding episodes.
- The number of injections and dose per injection of rFVIII Fc required to resolve a bleeding episode.
- rFVIII Fc incremental recovery (IR).
- Response to ITI with rFVIII Fc (complete success, partial success, failure, early withdrawal).

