Patients who fulfill the criteria for ITI complete success or 33 months of ITI treatment then transition to a “tapering” regimen over a minimum period of 12 weeks with the aim of starting a prophylactic rFVIII Fc regimen, and are monitored for relapse for up to 9 months.

Tapering visits are every 4 weeks (± 1 week) within a 12-week period.

Follow-up monitoring for relapse visits are every 12 weeks (± 2 weeks) within a 9 month period.

Surgery Visits

Surgery visits are as follows:

- Pre-Surgery Visit (Week -4 to Week -2). Not required for emergent surgery.
- Preoperative Assessment (Day of Surgery). If surgery is delayed by ≥ 8 weeks, preoperative assessments are to be repeated. These include assessments of FVIII activity and Nijmegen-modified Bethesda assay. For minor surgery, the Investigator will be in contact with the patient’s parent/caregiver to determine when the patient may return to the regular prophylactic treatment regimen.
- Postoperative Visit (1 to 2 weeks after surgery). Visit is required for major surgeries only.

- Last Postoperative Visit. This visit occurs when the Investigator determines that the patient can return to the regular prophylactic treatment regimen. This visit is not required if the return to the regular prophylactic treatment regimen occurs at the Postoperative Visit. If the patient is withdrawn from the study, then the patient completes the ET/EOT Visit assessments at least 2 weeks after surgery.

End-of-Treatment Visit

End of Treatment (EOT) for individual patients is defined as follows:

- Any individual patient who completes at least 50 EDs of rFVIIIIFc and is not on an ITI regimen has completed treatment.
- A patient undergoing ITI with rFVIIIIFc has completed treatment if either of the following occurs:
 - The patient achieves complete ITI success and completes the tapering and monitoring periods.
 - The patient completes 33 months on an ITI regimen without achieving complete ITI success (that is, ITI failure or partial ITI success).
- Individual patients may also be required to end treatment because one of the following has occurred:
 - The patient meets the criteria for early withdrawal.
 - Study stopping rules are met.
 - EOS is reached.

Final Safety Follow-Up Visit

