5.3.2. Categorical Variables

Categorical variables (e.g., ITI response) will be summarized using counts and percentages. All percentages will be rounded and presented to one decimal place, unless otherwise specified in the Statistical Programming Specifications for the study. The denominator for calculating percentages will depend on the variable to be summarized. For example, the denominator for calculating percentage of patients with any adverse event will be the Safety Analysis Set, which is number of patients dosed with rFVIIIFc.

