5.4.8. ITI Period

The ITI period is defined as the time from when a patient in the ITI sub-study begins this treatment regimen until they complete or withdraw from the study. The start of this period is the date and time of the first dose of the ITI regimen.

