7.4.9. Response to Immune Tolerance Induction (ITI)

The ITI Analysis Set will be analyzed for response to the treatment regimen. Possible treatment responses are:

Complete Success

All of the following criteria are met:

1. Negative inhibitor titers in 2 consecutive determinations at least 28 days apart
2. IR $\geq 66\%$ of baseline in 2 consecutive determinations at least 28 days apart
3. $t_{1/2} \geq 6$ hours

Partial Success

The determination of partial success will be made only for patients who have completed 33 months of ITI but who do not fulfill the criteria for complete success. To achieve partial success, the following criteria must be met after patients have completed 33 months of ITI:

- Negative inhibitor titers on 2 consecutive determinations at least 28 days apart AND
- Either of the following (but not both):
 - IR $\geq 66\%$ of baseline in 2 consecutive determinations at least 28 days apart, or
 - $t_{1/2} \geq 6$ hours

Failure:

ITI failure is defined as the inability to meet criteria for Complete Success or Partial Success after 33 months on ITI.

Early Withdrawal/ITI Ongoing:

Patients may withdraw from the study during the ITI period before reaching 33 months or complete or partial success. In addition, any patients still in the ITI sub-study at the time of EoS or interim analysis will be included in this category.

Response categories of complete success, partial success, failure, and early withdrawal will be presented overall for the ITI Analysis Set, and separately for the inhibitor subgroups specified in Section 5.1.2.5, namely:

- Patients with high-titer inhibitors
- Patients with low-titer inhibitors that meet the clinically meaningful criteria
- Patients with high-titer inhibitors or low-titer inhibitors that meet the clinically meaningful criteria

Patients fulfilling the criteria for complete success will transition to a “tapering” regimen over a minimum period of 12 weeks with the aim of starting a prophylactic rFVIII Fc regimen, as described in [Section 10.2.7.5](#) of the protocol, and will be further monitored for relapse for up to 9 months as described in [Section 10.2.7.6](#) of the protocol.

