During this period, the monitoring for relapse is via blood samples processed by the central laboratory using the Nijmegen-modified Bethesda assay for inhibitor detection, as well as IR assessments. The inhibitor titer and IR will be measured every 3 months during the follow up period. rFVIII Fc $t_{1/2}$ assessments will be performed 12 months after ITI success. If any of these tests reverse previously met criteria, at any time between the start of tapering through the beginning of prophylaxis, the tests must be repeated within 2 to 4 weeks to confirm relapse.

Relapse is defined as any of the following, occurring within 12 months following complete ITI success:

- A positive inhibitor (≥ 0.6 BU/mL using the Nijmegen assay) that is confirmed by a second test result of ≥ 0.60 BU/mL from a separate sample, drawn at least 2 weeks following the date that the original sample was drawn.
- 
- $t_{1/2} < 6$ hours.

The incidence of relapse during both the tapering and formal relapse monitoring period, in patients who are complete successes, will also be part of the summary.

A data listing will be generated for all patients in the ITI sub-study. This will include date of first inhibitor sample with a positive result, all inhibitor, IR, and $t_{1/2}$ measurements after commencement of ITI therapy, as well as dosing information. It will also include elapsed time to each assessment and a flag to indicate the patient’s ITI status.

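### The ITI response summary puts unfinished ITI courses in the same category as withdrawals, and the 12-month relapse incidence has no rule for complete successes whose follow-up is cut short (SAP 7.4.9)

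*SAP*

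**What the plan says.** SAP 7.4.9 lists four ITI outcomes. Complete success can be reached at any time. Partial success and failure can be declared only after 33 months of ITI. The fourth category is headed Early Withdrawal/ITI Ongoing. It takes patients who leave the study during ITI before an outcome, and then "any patients still in the ITI sub-study at the time of EoS or interim analysis will be included in this category".

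The sentence describing the table drops the second half of that heading: "Response categories of complete success, partial success, failure, and early withdrawal will be presented overall for the ITI Analysis Set". The endpoint list in SAP 2.2.2 uses the same short name, "Response to ITI with rFVIII Fc (complete success, partial success, failure, early withdrawal", as does protocol 6.2.2.

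Protocol 16.6 leaves further ITI reporting to the SAP: "Additional summaries, including the percentage of subjects with relapse". SAP 7.4.9 responds with "The incidence of relapse during both the tapering and formal relapse monitoring period, in patients who are complete successes", where relapse must occur within 12 months of complete success. Half-life below 6 hours is one relapse criterion, and the half-life test is scheduled 12 months after success. SAP 5.3.2 adds only the general statement that "The denominator for calculating percentages will depend on the variable to be summarized".

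**The concern.** A withdrawal is an outcome. A course still running at the data cut is an incomplete observation. Reporting both as one number, possibly under a name that describes only the first, can make ITI with this product look harder to stay on than it was. The reader also cannot tell how many courses were still undecided.

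The relapse figure has a related weakness. A success followed for a few months has had less opportunity to relapse than one followed for 12, and has not had the month-12 half-life test. If both count fully in the denominator, the proportion understates 12-month relapse. These are the main summary figures for the objective of describing ITI experience.

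**Working it through.** **1. The plan's own figure.** Protocol 7.3.2 gives 3 months of tapering plus 9 months of monitoring: 3 + 9 = 12 months after success, as stated there.

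**2. Can courses be cut off?** The longest path is 33 + 3 + 9 = 45 months from the start of ITI. Protocol 7.3 expects participation of about 6 months to 3 years (36 months), including the time before any inhibitor. Protocol 7.5 ends the study once at least 90 subjects reach 50 exposure days and brings in all ongoing subjects; it sets no condition on ITI. SAP 3.5 runs the same analyses at the interim unless indicated otherwise. Truncated courses are therefore plausible, and the wording of SAP 7.4.9 expects them.

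**3. Where does a truncated course go?** Before 33 months, partial success and failure are unavailable. A patient who is not yet a complete success can only fall in the pooled category.

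**4. Size of the pooled row.** The documents give neither the number of ITI starts nor the number ongoing at the cut, so all inputs are assumptions: 20 starts, 3 true withdrawals, k ongoing. Row = (3 + k)/20.

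| k ongoing | Row | True withdrawals |
|---|---|---|
| 0 | 3/20 = 15% | 15% |
| 2 | 5/20 = 25% | 15% |
| 5 | 8/20 = 40% | 15% |
| 8 | 11/20 = 55% | 15% |

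**5. Why the denominator should be stated when the row is split.** Assume 15 starts, 8 complete successes and 3 ongoing. Keeping everyone gives 8/15 = 53.3%. Dropping the ongoing patients gives 8/12 = 66.7%. A separate row should not become a reason to shrink the denominator.

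**6. Relapse.** Population (complete successes) and window (12 months) are given. A rule for shorter follow-up is not. SAP 5.3.3 names time to inhibitor as the only time-to-event variable, and none of the exceptions to no imputation in SAP 5.1.4 concerns relapse follow-up. Assume 8 successes and 1 observed relapse:

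- over all successes: 1/8 = 12.5% (exact 95% interval 0.3 to 52.7);
- if only 6 were followed for 12 months or relapsed earlier: 1/6 = 16.7% (0.4 to 64.1);
- if only 4: 1/4 = 25.0% (0.6 to 80.6).

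The first figure is biased low when follow-up is cut. The restricted figures lean high, because early relapses stay in while relapse-free patients who were cut drop out. Printing the counts lets a reader see how far apart the two are.

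**7. Can other outputs recover the split?** SAP 6.1 tabulates completed and discontinued patients with the primary reason, including for those ever on ITI, but at study level. Under protocol section 11, an inhibitor relapse during tapering or monitoring requires withdrawal, so such a complete success is withdrawn from the study although not an ITI withdrawal. The patient listing in SAP 7.4.9 holds every inhibitor, recovery and half-life result after the start of ITI, elapsed times and an ITI status flag, but the flag's levels are not defined. A reader could rebuild part of the split by hand.

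**The case against.** The strongest reply is that the SAP discloses the pooling in the category heading and definition, that the analysis is descriptive in what may be a small group, and that disposition reasons, the ITI key-visit table and the listing carry the missing detail. Much of this stands, and it is why the point is minor. The table shells are not in the documents, so the printed label is unknown and sub-rows cannot be excluded. The criticism is of the table as the SAP text describes it.

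Three stronger readings are tempting and are not supported.

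- *Relapse has no stated denominator.* A reader might infer this from the general wording of SAP 5.3.2, but SAP 7.4.9 names complete successes. Only the treatment of incomplete follow-up is missing.
- *Complete successes in tapering or monitoring would be counted as ongoing.* SAP 5.4.8 runs the ITI period "from when a patient in the ITI sub-study begins this treatment regimen until they complete or withdraw from the study", so read literally they are still in the sub-study. But SAP 7.4.9 reports relapse in those phases among complete successes, which works only if they keep that classification. A sentence saying so would clarify; it would not correct an error.
- *The relapse figure will be far too low.* No document supports a size. Inhibitor and recovery tests run throughout tapering and monitoring, so not every relapse depends on the month-12 half-life, and one criterion is redacted.

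**Conclusion.** The point holds, at minor severity. Followed as written, SAP 7.4.9 puts unfinished ITI courses and withdrawals in one category of a secondary endpoint's summary, and the planned outputs only partly allow them to be separated. The 12-month relapse incidence lacks a rule for successes with shorter follow-up; if it is a crude proportion of all successes, its bias is downward.

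The direction follows from the documents; the size does not. The rise from 15% to 40% rests on an assumed 20 starts, 3 withdrawals and 5 ongoing patients, and with none ongoing there is no distortion. The relapse percentages are equally illustrative, and their intervals show how little a group of that size could establish under any rule.

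**What to change.** In SAP 7.4.9:

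(a) Report ITI ongoing at data cut or end of study as its own row, separate from early withdrawal, with the full ITI Analysis Set as the stated denominator.

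(b) Report relapse as n over all complete successes, together with the number followed for the full 12 months (or relapsed earlier) and the number with a month-12 half-life.

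As clarification only, state that an outcome already determined is kept. Also reconcile the passages on patients who finish 33 months without complete success. SAP 5.1.2.2 says "Patients who fulfill the criteria for ITI complete success or 33 months of ITI treatment then transition" to tapering. Protocol 10.6, and the end-of-treatment list in that same SAP section, count such patients as having completed treatment, and SAP 7.4.9 describes tapering only for complete successes.

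The cost is a few sentences, one extra row and two counts in the already planned summary of ITI response and relapse. No new data are needed. A Kaplan-Meier estimate of relapse, or a cumulative incidence of success with withdrawal as a competing event, is optional and would be imprecise if few patients start ITI.

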7.5. Analysis of Exploratory Endpoint(s)

7.5.1. Health Outcomes

The health outcomes related to hemophilia in this study consist of the following items based upon the last month:

- How many times the child’s infusion/injection was administered by different persons/in different locations
- Whether the parent/caregiver missed any work due to the child’s hemophilia
- Whether the child missed any school due to their
- Whether the parent/caregivers social/leisure time became disrupted due to the child’s hemophilia

- Whether household/domestic routine was disrupted due to the child's hemophilia

Full details of the questionnaire can be found in [Appendix A](#). The data will be tabulated categorically at each visit for the FAS.

7.5.2. Physicians Global Assessment of Response

Investigators recorded assessments of each patient's response to their assigned rFVIII Fc regimen using the following 4 point scale:

- Excellent
- Effective
- Partially Effective
- Ineffective

The Investigators' assessments will be summarized by visit for the FAS.

The number and percentage of patients in each response category will be tabulated. Percentages will be based on the number of patients for whom an assessment was provided at the respective visit. This table will also include a cumulative tabulation across all scheduled study visits; patients can be included in this tabulation up to all visits, once for each visit. Percentages for this collection of responses throughout the study will be based on the total number of assessments across all visits. In addition, these assessments will be provided in a data listing.

7.5.3. Surgery

Only data from major surgeries will be summarized for the surgery subgroup of the Full Analysis Set. All data will also be listed and similar listings will be written for data from minor surgeries.

Date of admission for surgery, start/end time for surgery, the surgical procedure performed, blood loss during and post operation, blood products used (including transfusion details for type of transfusion, date administered and amount given), date of discharge from hospital, date of last surgery follow-up and the Investigators'/Surgeons' assessment of response to surgery measurements will be listed for all surgeries. Consumption on the day of surgery, including the number of injections required to maintain hemostasis, along with consumption and the number of injections administered over a 2-week period (Days 1-3, Days 4-14, and Days 1-14) following surgery will also be provided in a listing. The dosing intervals utilized during surgery will be characterized with the minimum and maximum intervals between injections required over this 2-week period.

7.5.3.1. Investigators'/Surgeons' Assessment of Patients' Response to Major Surgery

The Investigators'/Surgeons' assessment (using the 4-point surgery response scale detailed in Appendix 2) of the patient's hemostatic response to rFVIII Fc at 24 hours post-surgery will be summarized categorically and with descriptive statistics for all major surgeries for the FAS. Categorically, the number and percentage of surgeries given each rating will be tabulated. Percentages will be based on the number of surgeries for which a response was provided. Since

	Statistical Analysis Plan	Final v1.0
---	----------------------------------	-------------------

the response is given as an ordered ordinal scale, the responses have also been given a numeric score (Excellent=1, Good=2, Fair=3, Poor/none=4). A lower average score indicates a better Investigators’/Surgeons’ assessment of the patients’ response to surgery with rFVIII Fc. Descriptive statistics will be provided using the numeric value of the 4-point scale.

7.5.3.2. Number of Injections and Dose Required to Maintain Hemostasis During Major Surgery

The number of injections, the mean dose per injection (IU/kg), and the total dose (IU/kg) required to maintain hemostasis during surgery will be summarized for all major surgeries for patients in the FAS. The number of injections per surgery will be summarized categorically (0, 1, 2, 3, 4, >4) and with descriptive statistics. Percentages for the categorical summary will be based on the number of major surgeries. The mean dose per injection and total dose required to maintain hemostasis will be summarized using descriptive statistics. The mean dose per injection will be determined as the average dose across all injections per surgery (including the loading dose); the total dose will be determined as the sum across all injections (including the loading dose) per surgery.

7.5.3.3. Estimated Total Blood Loss and Transfusions Received during Major Surgery

The estimated total blood loss during and post each major surgical procedure will be summarized using descriptive statistics. These data will additionally be summarized for the number of transfusions per surgery (regardless of the type of transfusion), the number of transfusions summed across all surgeries for each type of transfusion, and the number of surgeries requiring each type of transfusion will be summarized categorically for all major surgeries for the FAS. Percentages in the categorical summaries will be based on the number of major surgeries for which the respective data is available.

7.5.3.4. Total rFVIII Fc Consumption per Major Surgery

Total consumption (IU/kg) per major surgery on the day of surgery, for the first 2 weeks following surgery (Days 1-3, 4-14, and 1-14), and for the overall surgical/rehabilitation period will be summarized using descriptive statistics for all major surgeries for the FAS. The day of surgery refers to the calendar day of the surgery and includes the loading dose given for that surgery. The first 2 weeks following surgery begins the day after surgery and extends for 14 calendar days. The overall surgical/rehabilitation period is defined in Section 5.4.3. Total rFVIII Fc consumption will be determined as the sum of all doses administered during the referenced time periods.

7.5.3.5. Summary of Bleeds per Major Surgery

The total number of bleeding episodes per major surgery during the surgical/rehabilitation period will be summarized categorically (0, 1, 2, 3, >3) and with descriptive statistics. The total number of surgeries with a bleeding episode with onset during Days 1 to 3, Days 4 to 7, Days 8 to 14, and Days 15 to 28 during the surgical/rehabilitation period will be summarized categorically for all major surgeries for the FAS. A surgery will be included in each interval of time for which

	Statistical Analysis Plan	Final v1.0
---	----------------------------------	-------------------

there was a bleeding episode that started during that time interval. If a bleeding episode started and resolved and another bleeding episode then started within a given time interval, that surgery will be counted only once in that interval. A bleeding episode that starts in one time interval and continues into the next one will be counted only in the interval in which it started. Percentages for this summary will be based on the number of patients still in the surgical/rehabilitation period during the respective interval of time.

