5.1. General Principles

In general, the following approaches will be used in analysis/summary of baseline/demography, safety, efficacy and exploratory endpoint data, unless otherwise specified in this SAP.

Data will be summarized using standard summary statistics for continuous and categorical data, as appropriate (additional information is provided in Section 5.3).

No statistical hypothesis testing is planned. However, 95% confidence intervals (CIs) when determined for a binomial proportion will use the Clopper-Pearson method.

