5.4.3. Surgical/Rehabilitation Period

The broadest span of time for the surgical/rehabilitation period is from the first dose of rFVIIIFc given for the surgery (i.e., the pre-surgery dose) up to 1 minute before the first regular prophylactic dose after the last day of postoperative care/rehabilitation. Since not all patients will have these events, specific considerations for the start and end of the surgical/rehabilitation period are as follows:

Start of the surgical/rehabilitation period:

- If there is more than one pre-surgical dose then the first one should be selected (a pre-surgical dose can be administered the day before the surgery).
- If there is no pre-surgical dose but there was a prophylactic dose the day before surgery, this prophylactic dose should be selected.
- If there is no pre-surgical dose or a prophylactic dose the day before surgery then select the start date/time of the surgery. If the time was not recorded then select the date and impute 00:01 for the time.

End of the surgical/rehabilitation period:

- 1 minute before the first prophylactic dose on or after the last date among the dates for discharge from the hospital, post-operative visit 1, post-operative visit 2, and the end of rehabilitation.
- If all of the dates mentioned above are missing, then select the first prophylactic dose after the date/time for the end of surgery. If the surgery time was not recorded then select the surgery date and impute 23:59 for the time. If the end date of the surgery is missing then select the start date of the surgery and impute 23:59 for the time.

- If there are no prophylactic doses following the latter of the 5 dates mentioned above, then select the latter of the dates and impute 23:59 for the time if otherwise there is no time associated with the given date (e.g., the patient completed the surgical/rehabilitation period but received no further prophylactic doses).
- If the overall end of study is declared while the patient is still in the surgical/rehabilitation period then select the date of the end-of-study visit and impute 23:59 for the time if a time is not provided.

Two exceptions are noted:

- If 2 (or more) major surgeries are performed without an intervening discharge from the hospital, then the first surgical/rehabilitation period will end 1 minute before the start of the next surgery and the second surgical/rehabilitation will end as described above.

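### The post-surgery interval bleeding table (SAP 7.5.3.5) counts major surgeries but divides by patients, so an interval's percentage is inflated if one child has two or more major surgeries at risk in it

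*SAP*

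**What the plan says.** SAP 7.5.3.5 contains two summaries. The first gives bleeding episodes per major surgery over the whole surgical/rehabilitation period, in categories 0, 1, 2, 3 and >3. The second is by interval and is introduced as "The total number of surgeries with a bleeding episode with onset during Days 1 to 3", followed by Days 4-7, 8-14 and 15-28. The counting rule for the second is also per surgery: where bleeds recur within one interval, "that surgery will be counted only once in that interval". Nothing limits the count to one per patient.

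The section ends with the percentage base: "Percentages for this summary will be based on the number of patients still in the surgical/rehabilitation period during the respective interval of time". The reference to the respective interval ties this sentence to the second summary only.

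The neighbouring surgery sections use surgeries as the base:
- 7.5.3.1 (response): "Percentages will be based on the number of surgeries for which a response was provided".
- 7.5.3.2 (injections): "Percentages for the categorical summary will be based on the number of major surgeries".
- 7.5.3.3 (transfusions): "Percentages in the categorical summaries will be based on the number of major surgeries for which the respective data is available".

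SAP 5.4.3 provides for repeat operations in one child. It has a rule that begins "If 2 (or more) major surgeries are performed without an intervening discharge from the hospital", under which the first period closes 1 minute before the next surgery and the next surgery has its own period.

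**The concern.** A percentage is interpretable when everything counted on top is also counted underneath. Here a child with two major surgeries can add two to the numerator of an interval but only one to its denominator. The result is neither the share of surgeries with a bleed nor the share of children with a bleed.

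Perioperative efficacy is an exploratory objective (Protocol 6.1.3, SAP 2.1.3). SAP 5.4.2.1 takes surgical/rehabilitation periods out of the efficacy period on which the bleeding rates are based, so 7.5.3.5 is where bleeds in those periods are summarised. If few major surgeries occur, one repeat operation could visibly move an interval's percentage.

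**Working it through.** The documents state no figure for this table, so there is nothing to reproduce. The check is on the rule itself.

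**Definitions, for one interval**
- *b* = major surgeries with a bleed starting in the interval (numerator, SAP 7.5.3.5)
- *P* = distinct patients still in a surgical/rehabilitation period (denominator as written)
- *S* = major surgeries whose surgical/rehabilitation period is still open (denominator in the numerator's own unit)

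**Formulas**
- As written: 100 × b / P
- Same unit above and below: 100 × b / S
- Ratio of the two: (b / P) ÷ (b / S) = S / P

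Every patient at risk has at least one surgery at risk, so S / P is never below 1. It equals 1 when each child has one surgery at risk. The percentage as written exceeds 100% exactly when b > P. Since b cannot exceed S, this needs S > P, but S > P alone is not enough.

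**Illustrations.** All counts are assumed, because the documents give none.

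| Patients P | Surgeries S | With a bleed b | As written b/P | Surgery base b/S | S/P |
|---|---|---|---|---|---|
| 5 | 5 | 2 | 40.0% | 40.0% | 1.00 |
| 4 | 5 | 1 | 25.0% | 20.0% | 1.25 |
| 4 | 5 | 2 | 50.0% | 40.0% | 1.25 |
| 3 | 5 | 4 | 133.3% | 80.0% | 1.67 |
| 1 | 2 | 2 | 200.0% | 100.0% | 2.00 |

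The second and third rows have repeat surgery and inflation but stay well below 100%. The last two pass 100% because b exceeds P.

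**Effect of the 5.4.3 truncation rule.** Suppose a second major surgery, without discharge, falls within Days 4-7 of the first.
- Days 1-3: both surgeries had an open period in their own Days 1-3, so the child contributes S = 2 and P = 1.
- Days 8-14 and 15-28: the first period has closed, so the child contributes at most one surgery and the two bases agree for him.

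If instead the child is discharged between operations, the truncation rule does not apply, and both surgeries can be at risk in later intervals too. The condition that matters is therefore two or more surgeries in one child at risk in the same relative interval.

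**The case against.** The strongest reply is that this is loose wording. The section is headed as a per-surgery summary and 5.4.3 defines the period per surgery, so a programmer could build one record per surgery period and count those records as patients. The problem would then vanish. That is possible, but the text does not say it. Where the SAP wants one patient counted repeatedly, it says so: the cumulative table in 7.5.2 admits a patient once per visit and uses total assessments as the base. Nothing similar appears in 7.5.3.5, so the benign result requires departing from the written rule.

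Several limiting points stand:
- The per-surgery summary (0, 1, 2, 3, >3) does not use this denominator, and the interval counts are correct as counts.
- Repeat major surgery may be rare. Protocol 10.2.8.1 defines major surgery narrowly and classes port placement as minor. The rule in 5.4.3 is a contingency and does not show that repeats are expected.
- The endpoint named for surgery, the Investigator/Surgeon's assessment, already uses a surgery base (7.5.3.1).
- SAP section 12 lists bleeding episodes for the first 14 days after major surgery, so the intervals to Day 14 could be recomputed by surgery.

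A reader might also infer that the whole table is not comparable with its neighbours. The documents do not carry that far. Those tables measure different things, and even with the right unit the interval table keeps an at-risk base that shrinks over time.

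**Conclusion.** The unit mismatch is explicit, and no other section redefines the word *patients*. The written rule gives a wrong percentage for any interval in which a child has two or more major surgeries at risk. The inflation factor is S/P, for example 1.25 with an assumed 5 surgeries in 4 children.

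A reader might infer more: that post-operative bleeding is overstated as a matter of course, or that any repeat surgery pushes the percentage past 100%. The documents support neither. With one major surgery per child the factor is 1.00, and passing 100% also needs surgeries with a bleed to outnumber the distinct patients at risk. How often either condition arises cannot be judged from the documents.

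The consequence is minor. Only the four interval percentages are exposed, the objective is exploratory, "No statistical hypothesis testing is planned", and the primary inhibitor endpoint is untouched.

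**What to change.** In the last sentence of SAP 7.5.3.5, replace *patients* with *major surgeries*, so that the base is the number of major surgeries whose surgical/rehabilitation period is still open during the interval. It would help to state that a surgery counts if its period is open at any point in the interval. Every surgery in the numerator is then also in the denominator, and the percentage cannot exceed 100%.

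This keeps the at-risk logic and matches the unit in 7.5.3.1 to 7.5.3.3. The cost is one word in the SAP and a matching line in the table program. No new data are needed, and the results do not change if no child has more than one major surgery at risk in an interval.
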